7. RESEARCH QUESTION AND OBJECTIVES

This study consists of compiling and analyzing recent data from a customized retrospective medical record review conducted in 7 countries (Argentina, Brazil, Colombia, Costa Rica, Ecuador, Mexico, and Peru) to assess the following primary objectives:

- Describe demographic and clinical characteristics of patients in Latin America diagnosed with metastatic RCC who received first-line sunitinib and switched from the 4/2 to the 2/1 schedule.
- Characterize detailed first-line sunitinib treatment patterns, including dose, schedule, total duration of sunitinib treatment, duration on the 4/2 schedule, duration on the 2/1 schedule, reasons for stopping treatment lines, and supportive care.

The secondary objectives of the study will include an exploration of clinical outcomes (ie, response to treatment, AEs, PFS, and overall survival) after switching to the 2/1 schedule. Switching to the 2/1 schedule is a relatively new occurrence in the studied countries, resulting in limited available follow-up time to observe clinical outcomes among patients who switched to the alternative schedule. Furthermore, this study relies on a convenience sample of sites treating patients at a select number of treatment centers, will provide only descriptive information on observed events, and is designed to generate, not test, hypotheses. In Brazil, early feasibility results suggest physicians frequently prescribe sunitinib on the 2/1 schedule at first-line initiation; therefore, secondary objectives will also include a descriptive exploration of demographic, clinical and treatment characteristics (eg, duration of treatment, reasons for stopping treatment), and clinical outcomes (eg, treatment response, AEs, PFS, and overall survival) among patients initiating first-line sunitinib on the 2/1 schedule. It is anticipated this sample will be relatively small. Secondary objectives will be assessed with known limitations concerning data availability and generalizability of the findings.

8. RESEARCH METHODS

[figure not shown]
To achieve the study objectives described in Section 7, PPD, a research consultancy specializing in conducting multinational real-world health economic and outcomes studies, will analyze retrospective medical record data from 150 patients who received care at treatment centers across 7 Latin American countries. Prior to initiation of data collection activities, PPD, in consultation with Pfizer Inc. (Pfizer), will develop a customized case report form (CRF) to capture detailed data on demographics, clinical characteristics, treatment patterns, AEs, and health outcomes from eligible patients' medical records. The length of the CRF will be consistent with an abstraction time burden of approximately 30 to 45 minutes. After selection of potential sites by Pfizer, PPD will work with the sites to assess feasibility of the site's participation by using a site information form. If the study is determined to be feasible at a specific site, the principal investigator (PI) and their designated research team at the participating site will obtain the necessary ethics approvals for conducting this study. In countries where national ethics activities are required, a lead site in the relevant country will be selected to support the national

submission. Specific responsibilities to be conducted and coordinated by Pfizer, PPD, and individual sites during the site identification, feasibility assessment, contracting process, and data collection are shown in Figure 1.

Following receipt of the required ethics approvals, the site PI and/or designated research team will be provided a link(s) to the secure electronic CRF (eCRF) to enter the abstracted data electronically. The PI may personally abstract data and/or designate their research team to abstract data. Once a potential medical record is identified, the abstractor will answer multiple screening questions in the eCRF to confirm the selected medical record is eligible for inclusion. Next, the abstractor will complete the eCRF by retrospectively reviewing all available data in the patient's medical record.

During the data collection phase, PPD will monitor recruitment and data collection activities. Upon completion of data collection, PPD will perform the analyses required to address Pfizer's study objectives. One interim analysis on partial data may be conducted upon Pfizer's request. Finally, PPD, in consultation with Pfizer, will develop a study report presenting the study methods, the CRF, the study results in the form of relevant tables and figures, and an interpretation of the results.

Figure 1. Site Selection, Feasibility Assessment, Contracting, and Data Collection Responsibilities

AE = adverse event; CDA = confidential disclosure agreement; CRF = case report form; PI = principal investigator; PPD .

[figure not shown]
PFIZER CONFIDENTIAL

8.1. Study Design

This study is a retrospective, observational medical record review of adult patients with metastatic RCC. A sample of 150 records of patients who meet the eligibility criteria described in [Section 8.2.1](#) will be targeted. Data describing patient and clinical characteristics, first-line treatment patterns, AEs, and clinical outcomes will be abstracted directly by the PI and/or their designated research team. This study is descriptive, with the primary goal of retrospectively summarizing existing sunitinib treatment patterns and patient outcomes. As the data collected will be retrospective, the conduct of this study will in no way influence prescribed treatment. [Figure 2](#) presents a graphical summary of the study design for patients who switched from the 4/2 to 2/1 schedule. [Figure 3](#) displays a summary of the study design for the sample of patients in Brazil who initiated first-line sunitinib on the 2/1 schedule.

The primary measures of interest are described in [Section 8.3](#).

Figure 2. Study Design: First-Line Switch From 4/2 to 2/1 Sunitinib

[figure not shown]

RCC = renal cell carcinoma.

Note: The end of study follow-up may be contingent on country-specific or site-specific ethics requirements, for example, the last date of available data on the date of ethics approval at a given site. Patients may have a gap between stopping the 4/2 schedule and starting the 2/1 schedule.

PFIZER CONFIDENTIAL

Figure 3. Study Design: Initiated First-Line 2/1 Sunitinib (Brazil Only)

RCC = renal cell carcinoma.

Note: The end of study follow-up may be contingent on country-specific or site-specific ethics requirements, for example, the last date of available data on the date of ethics approval at a given site.

8.2. Setting

Data for this study will be abstracted from the medical records of patients treated for metastatic RCC at approximately 17 treatment centers (ie, sites) in 7 countries: Argentina, Brazil, Colombia, Costa Rica, Ecuador, Mexico, and Peru.

8.2.1. Patient Inclusion Criteria

1. Diagnosed with metastatic RCC with clear cell histology:
 - a. The patient may have been initially diagnosed with Stage IV or initially diagnosed at an earlier stage and progressed to having disease at distant sites (ie, metastatic disease).
2. Initiated first-line treatment for metastatic RCC with sunitinib on the 4/2 schedule (all countries) or initiated first-line treatment for metastatic RCC with sunitinib on the 2/1 schedule (Brazil only).
3. Switched to the 2/1 schedule (all countries) or initiated the 2/1 schedule (Brazil only) during the first treatment line between January 1, 2014, and June 30, 2018:
 - a. The final dates defining this selection period will be dependent on country-specific ethics and reporting requirements.
4. Aged 18 years or older at the time of the switch to the 2/1 schedule (all countries) or initiation of the 2/1 schedule (Brazil only).

PFIZER CONFIDENTIAL

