metastatic RCC (among other patients), reported similar adverse event mitigation with the 2/1 schedule and treatment duration more than three times longer than those who received the 4/2 schedule.⁶ Longer duration translates to longer dose maintenance, which improves clinical outcomes.

Despite the potential benefit from a modified treatment schedule evidenced in studies among patients in the United States and Europe, real-world clinical outcomes among patients receiving the 2/1 schedule for metastatic RCC in Latin America are unexplored.^{5,9} Further research on current, real-world clinical outcomes in this population may assist in providing additional context on the types of patients who may benefit from this alternative schedule.

The aim of the present study is to describe clinical characteristics, treatment patterns, and clinical outcomes (eg, PFS, change in prevalence of AEs) of adult patients with metastatic RCC in Latin America who received first-line sunitinib on the 4/2 schedule and then switched to the 2/1 schedule. In Brazil, feasibility assessments indicate many physicians start patients on the 2/1 schedule upon initiation of sunitinib for metastatic RCC. To reflect the patient population in Brazil, a second sample of patients who initiated first-line sunitinib on the 2/1 schedule will be collected and analyzed separately. As patient characteristics, prescribing patterns, health care systems, and access to care in community practice settings differ from highly controlled clinical trial environments, clinical outcomes (eg, treatment response, PFS, overall survival) in real-world patient populations may vary from published trials. As current research on health outcomes among patients who received sunitinib on a 2/1 schedule for metastatic RCC in these countries is absent, there is a lack in understanding as to whether the alternative treatment schedule is safe and effective in patients in Latin America.

Results from this study may aid in the following:

- Understanding characteristics of patients who switched from a 4/2 to a 2/1 sunitinib schedule or initiated the 2/1 schedule in Brazil, and the resulting clinical outcomes in the real-world setting.
- Describing the occurrence of AEs on the 4/2 and 2/1 schedules.
- Providing real-world, baseline measures of contemporary prescribing patterns and health outcomes to which future innovations in therapy could be compared.

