8.2.2. Exclusion Criteria

1. Evidence of other malignant neoplasms (except nonmelanoma skin cancer or carcinoma in situ) within 5 years before switching to the sunitinib 2/1 schedule (all countries) or initiation of the 2/1 schedule (Brazil only).

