8.3.4. Treatment-related Outcomes

Treatment-related AEs (eg, hypertension, neutropenia, thrombocytopenia, fatigue, stomatitis) will be documented for the duration of first-line treatment with sunitinib. Frequency of toxicity evaluation (eg, every 6 weeks) and the method of evaluation (eg, radiological evaluations by computed tomography, magnetic resonance imaging with measurable lesions via Response Evaluation Criteria in Solid Tumors [RECIST]) will also be documented.

Dates of progression and death (ie, whether the patient died during the follow-up period and whether the death was related to RCC) will be documented. Disease progression and survival estimates will be derived from these measures and calculated from the date of diagnosis of metastatic RCC, the start of first-line treatment line with 4/2 or 2/1 sunitinib, and the time of switch to the 2/1 schedule (among those who initiated on the 4/2 schedule). Survival estimates will include, but are not limited to, the following:

[figure not shown]
- Overall survival;
- PFS;
- Time to second-line initiation.

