8.7. Data Analysis

All measures described in [Section 8.3](#) will be summarized descriptively through the tabular and graphical display of mean values, medians, ranges, and standard deviations of continuous variables of interest and frequency distributions for categorical variables. Time-to-event outcomes (ie, overall survival, PFS, time to second-line initiation) will be described using the Kaplan-Meier method. All analyses will be conducted using SAS (version 9.4 or later) statistical software. Samples of patients who switched from the 4/2 to the 2/1 schedule from each country will be pooled and analyzed in aggregate. The sample of patients from Brazil who initiated first-line sunitinib on the 2/1 schedule will be analyzed separately. Results may be described for up to 2 subgroups that will be determined after the initial review of the data (eg, number of cycle on the 4/2 schedule).

As this study is descriptive and designed to generate hypotheses, direct comparisons between outcomes on the 4/2 schedule and on the 2/1 schedule will not be conducted. Potential confounders, such as characteristics that prompt the switch and other possible time-dependent factors (eg, dose modifications and delays), are not comprehensively collected or controlled for in this study design. Variability in timing of the switch from a 4/2 to a 2/1 schedule will affect the distribution of time-dependent outcomes after the switch (even in the absence of immortal-time bias), as some patients may switch “early” in their first-line therapy and others may switch “later.” Thus, causal inferences about the benefit of switching treatment schedules cannot be drawn.

PFIZER CONFIDENTIAL

Detailed methodology for summary and statistical analyses of data collected in this study will be documented in a statistical analysis plan, which will be dated, filed and maintained by the sponsor. The statistical analysis plan may modify the plans outlined in the protocol; any major modifications of primary endpoint definitions or their analyses would be reflected in a protocol amendment.

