8.9. Limitations

Retrospective medical record reviews are subject to the following general limitations:

- Patients selected for study inclusion represent a “convenience” sample, in that the records will be obtained from sites who are willing to participate in the study. Therefore, study findings may not be generalizable to the overall population of patients with metastatic RCC or sites where RCC is treated in the selected countries.
- All data captured in the eCRF will be limited to information available in the patients’ medical records held by the sites participating in the study. Information on health care services received outside the sites’ care setting that is not recorded in the medical record will be unavailable for this study (eg, treatment for AEs received through a separate hospital).
- To increase the chance of random selection of eligible medical records at sites that estimate a larger than needed eligible population, abstractors will be asked to select medical records for patients whose last names begin with a randomly generated letter between A and Z. Due to variations in the distribution of first letters among last names, patients may not have an equal probability of inclusion in the study.
- Data will be entered directly by each site’s research team or PI and therefore may be subject to entry errors and resulting inaccuracies in reporting. Although there will be data checks in place to improve internal consistency of the data, responses will not be validated against the patients’ medical records by an independent reviewer.
- This study is designed to describe characteristics and outcomes of patients who switched from the 4/2 to the 2/1 sunitinib schedule. Potential confounders, such as characteristics that prompt the switch and other possible time-dependent factors (eg, dose modifications and delays), are not comprehensively collected or controlled in this study design. Variability in timing of the switch from a 4/2 to a 2/1 schedule will affect the distribution of time-dependent outcomes after the switch (even in the absence of immortal-time bias), as some patients may switch “early” in their first-line therapy and others may switch “later.” Thus, causal inferences about the benefit of switching treatment schedules cannot be drawn.

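### The plan neither requires nor records whether the site's record covers the 4/2 period, so 4/2 adverse events could be under-counted by an amount nobody can measure

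*Combined protocol and SAP*

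**What the plan says.** **Eligibility.** The switch sample is defined in section 8.2.1 by clear cell metastatic RCC, "Initiated first-line treatment for metastatic RCC with sunitinib on the 4/2 schedule (all countries", a switch to 2/1 "during the first treatment line between January 1, 2014, and June 30, 2018", and age 18 or older at the switch. The single exclusion in 8.2.2 is "Evidence of other malignant neoplasms (except nonmelanoma skin cancer or carcinoma in situ) within 5 years before switching to the sunitinib 2/1 schedule" (or before starting 2/1, in the Brazilian sample). None of these says where the 4/2 treatment was given or whether the site holds the record of it.

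**Data on the 4/2 period.** Under section 8.3.4, treatment-related AEs "will be documented for the duration of first-line treatment with sunitinib", which includes the time on 4/2. Section 8.3.3 collects 4/2 start and stop dates, daily doses with dated changes and reasons, and best response separately for each schedule. Supportive care is collected over the whole first line.

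**Intended use.** Section 6 lists "Describing the occurrence of AEs on the 4/2 and 2/1 schedules" among the uses of the results and gives "clinical outcomes (eg, PFS, change in prevalence of AEs" in its statement of aim.

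**Analysis and limitations.** Section 8.7 plans "frequency distributions for categorical variables" and leaves detailed methods to a separate statistical analysis plan. Section 8.9 concedes that information on care received elsewhere "that is not recorded in the medical record will be unavailable for this study".

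**The concern.** A patient may take 4/2 at one hospital and move to a participating site at about the time of the switch. If the new site's record shows that 4/2 was started and when the switch took place, the patient meets every listed criterion. The record may still hold little or nothing on toxicity and dose changes during 4/2.

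The listed variables include no date of first care at the site and no indicator of record coverage, so such patients look like any other. An empty 4/2 AE field can then mean either that no AE occurred or that nobody at this site could have seen it. The plan does not say how the two are told apart, or which denominator the 4/2 AE frequencies use.

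At stake is the description of AEs on 4/2 and any change in prevalence read from it. Counts of 4/2 dose changes are exposed in the same way, and dose is part of the second primary objective.

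**Working it through.** The plan derives no figure on this point. The 150 records are a convenience target without a power calculation (8.5), so there is nothing to reproduce. The check has three parts.

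**1. Can an uncovered patient be included and go unnoticed?** Sections 8.2.1 and 8.2.2 contain no coverage requirement. Sections 8.3.1 to 8.3.4 contain no coverage variable. Sections 8 and 8.4 mention eCRF screening questions, but only as a means of confirming eligibility. Under 8.6.7 neither the sponsor nor the vendor sees the medical records, and under 8.9 entries are not independently checked against them. On the protocol text, the answer is yes.

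**2. How large could the effect on 4/2 AE frequency be?** Let p be the true 4/2 prevalence of an AE and u the share of switch patients whose 4/2 period is outside the site's record. If those patients are tabulated as AE-free, and coverage is unrelated to toxicity:

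observed prevalence = p × (1 − u)

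Inputs: p = 12% is the Grade 3 hypertension rate for sunitinib quoted in section 6; p = 50% is an assumed rate for a commoner, any-grade event. The documents do not give u; 5% to 30% is assumed.

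| u | p = 12% | shortfall | p = 50% | shortfall | covered n of 150 |
|---|---|---|---|---|---|
| 5% | 11.4% | 0.6 points | 47.5% | 2.5 points | about 142 |
| 10% | 10.8% | 1.2 points | 45% | 5 points | 135 |
| 20% | 9.6% | 2.4 points | 40% | 10 points | 120 |
| 30% | 8.4% | 3.6 points | 35% | 15 points | 105 |

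The last column assumes that all 150 records are switch patients.

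For scale, the 95% half-width, 1.96 × √(p(1 − p)/n), at n = 150 is 5.2 points for p = 12% and 8.0 points for p = 50%. The shortfall stays within sampling error for the rarer event over the whole range of u. For the commoner event it exceeds sampling error at u = 20% (10 against 8.0).

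The formula is a worst case, because it assumes that no AE of an uncovered patient is captured. If a fraction c reaches the record through referral notes, observed prevalence is p × (1 − u(1 − c)). With u = 20% and c = 50%, 12% shows as 12% × 0.9 = 10.8% rather than 9.6%.

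**3. Which other 4/2 items are affected, and how?**

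- Dose changes: a change made elsewhere and not recorded may be counted as no change, so the same dilution is possible.
- Daily dose and best response: these are a recorded value and an assessed category. Without a record they are missing; they do not default to a low value, and the formula does not apply.
- Supportive care: no 4/2-specific figure is planned, so only the whole-first-line total could be low.

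**Direction.** If true prevalence is equal on both schedules and only 4/2 is diluted, 2/1 looks worse by p × u: 0.6 to 3.6 points at 12%, and 2.5 to 15 points at 50%.

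**The case against.** The strongest reply is that the plan states no rule treating an unrecorded AE as absent. The quality checks in 8.8 imply that abstractors can answer that data are unknown or unavailable, and gaps in the 4/2 dates and doses would show as missing data. The CRF is not in the documents, so a coverage question may yet be asked. This is correct as far as it goes. A reader might infer that transferred patients will be counted as AE-free; the documents do not support that as fact. It remains a possibility that the plan does not close, since 8.7 gives neither a denominator nor a missing-data rule for AEs.

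A reader might also infer that the loss is confined to 4/2 and that the 2/1 period is fully observed. Nothing in the documents says so. The limitation in 8.9 covers outside care at any time, including after the switch.

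On importance, the AE objective for switch patients concerns the period after the switch. The change in AE prevalence appears only as an example in section 6, 8.7 rules out direct comparison and causal inference, and 8.9 discloses the limitation in general terms. All of this stands and lowers the weight of the point. It does not remove it: the 4/2 frequency is a reported result in its own right, and a general disclosure does not let anyone count the patients affected.

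Deferral to a later analysis plan does not fully answer the point either. That plan can set a denominator, but it cannot use a coverage variable that was never abstracted.

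**Conclusion.** The point holds as a gap in data collection and in the denominator rule. Record coverage of the 4/2 period is neither required nor recorded, and no rule separates absence of an AE from absence of information.

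The size is unknown, because the documents give no share of transferred patients. Under the assumed 5% to 30%, and only if uncovered patients are tabulated as AE-free with nothing captured, a 12% rate would be understated by 0.6 to 3.6 points and an assumed 50% rate by 2.5 to 15 points.

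A reader might take this as a bias that flatters the switch to 2/1. It would do the opposite, by making 4/2 appear better tolerated. Nor does it call for excluding patients. It is an inexpensive improvement to a descriptive study, worth making because it cannot readily be made once abstraction is over.

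**What to change.** Before abstraction starts, add one eCRF item: *Does this site's record cover first-line sunitinib from the first 4/2 dose? If no, first date covered.*

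In section 8.7, state that 4/2-period AEs, dose changes and best response are reported among patients whose record covers that period, with the number uncovered shown beside each table. State also that an AE not recorded in an uncovered period is missing, not absent. Uncovered patients remain in the study for baseline characteristics, switch date and post-switch outcomes.

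The cost is one question per record and a smaller n in the 4/2 tables: 135 to 105 of 150 at an assumed 10% to 30% uncovered, if all 150 are switch patients. At n = 120 the 95% half-width for a 12% rate widens from 5.2 to 5.8 points. Restricting the denominator removes the dilution only if coverage is unrelated to toxicity. If patients transfer because of toxicity, the covered group is a selected one, so the uncovered number should be reported and this caveat stated. If almost everyone is covered, little is lost and the 4/2 results can be shown to be sound.

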8.3.3. Treatment Patterns

Measures related to the treatment of RCC before (if applicable) and after diagnosis of metastatic RCC will be gathered. [Figure 2](#) graphically depicts the time periods during which treatment patterns will be assessed for each sample. Treatment measures may include the following:

- Receipt of broad categories of treatment approaches, including neoadjuvant treatment(s), surgery, and adjuvant therapy before the diagnosis of metastatic RCC:
 - Date of receipt of last cancer-direct treatment before the diagnosis of metastatic RCC.
- Total number of systemic lines of treatment after the diagnosis of metastatic RCC:
 - Start and stop dates of each treatment line (duration of each treatment line will be calculated).
- Specific details regarding first-line treatment with sunitinib after the diagnosis of metastatic RCC include the following (where relevant to the specific sample):
 - Start and stop dates of the 4/2 schedule (duration of 4/2 treatment);
 - Date of switch to or initiation of the 2/1 schedule and stop date (duration of 2/1 treatment);
 - Time between stopping the 4/2 schedule and initiating the 2/1 schedule;
 - Reason for switch to 2/1 schedule;
 - Date of subsequent changes in schedule, if any
 - Reason for subsequent changes in schedule, if any
- Initial and subsequent daily dose(s) of sunitinib on the 4/2 and 2/1 schedules:
 - Date(s) of dose change(s), if applicable;

PFIZER CONFIDENTIAL

- Reason for change(s) in dose, if applicable.
- Reason for stopping treatment with sunitinib (eg, AE, progressive disease);
- Best clinician assessed response to treatment with sunitinib on the 4/2 schedule and best response on the 2/1 schedule.
- Receipt of broad categories of supportive care elements (medications and procedures) such as nutritional supplements, pain medications, antibiotics, antifungals, iron supplements, antiemetics/antinauseants, antidiarrheals, antivirals, radiation therapy, bone-targeting agents (eg, bisphosphonates, denosumab), erythropoiesis-stimulating agents, granulocyte-colony stimulating factors, folic acid, red blood cell transfusion, and platelet transfusion during the first line of treatment with sunitinib.

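### Eligibility dates only the switch to 2/1, so pooled 4/2 duration and time to switch depend partly on the calendar, by an amount and in a direction the documents do not fix

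*Combined protocol and SAP*

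**What the plan says.** Criterion 3 of section 8.2.1 requires the switch to fall "during the first treatment line between January 1, 2014, and June 30, 2018". Criterion 2 requires first-line sunitinib to have begun on 4/2 but carries no date. Criterion 3a makes the window provisional: "The final dates defining this selection period will be dependent on country-specific ethics and reporting requirements". The note to Figure 2 allows a gap between stopping 4/2 and starting 2/1.

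The second primary objective in section 7 includes "total duration of sunitinib treatment, duration on the 4/2 schedule, duration on the 2/1 schedule". The abstract adds time from 4/2 to 2/1 to the planned summaries, and section 8.3.3 collects the dates needed for both. On analysis, section 8.7 states: "Samples of patients who switched from the 4/2 to the 2/1 schedule from each country will be pooled and analyzed in aggregate". It permits up to two subgroups, chosen after a first look at the data, and gives the number of 4/2 cycles as an example.

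Section 7 also says: "Switching to the 2/1 schedule is a relatively new occurrence in the studied countries". Section 6 lists among the intended uses: "Providing real-world, baseline measures of contemporary prescribing patterns and health outcomes to which future innovations in therapy could be compared".

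**The concern.** Entry is decided by when a patient switched, while the quantity summarised is the time leading up to that switch. Someone who began 4/2 well before 2014 can enter only through a switch in 2014 or later, so early starters in the sample have long times to switch by construction. Someone who began in spring 2018 can enter only by switching within weeks. The pooled summary mixes these groups.

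If 2/1 was hardly used before the window opened, some of the long 4/2 durations reflect when the alternative reached the region, not how long patients now stay on 4/2. The observations are real; the issue is what their summary represents. It bears on a primary-objective measure and on the contemporary baseline that section 6 promises. Sections 8.7 and 8.9 do discuss variable timing of the switch, but only for outcomes after it.

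**Working it through.** **Inputs.** From the documents: a window of 54 months (4 × 12 + 6); median PFS of 11 months on sunitinib (section 6), borrowed here as an assumed median for leaving 4/2 without switching; a target of 150 records (section 8.5). Assumed, because the documents are silent: the monthly switch rate h (0.03, 0.05, 0.10), the date switching began, the trend in starts, starts from 2006 onward, identical patients with constant rates, and no gap between schedules (so 4/2 duration equals time to switch). The plan gives no expected 4/2 duration, so there is no figure of its own to reproduce.

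**1. Stable pattern.** Let starts be flat at rate r, and let f(d) be the unchanging density of switching after d months. At any calendar time, switches with duration d occur at rate r·f(d). The pooled in-window durations therefore follow f(d) exactly. Simulation agrees: true means of 3, 6 and 12 months give pooled means of 3.00, 5.99 and 12.00. Pre-2014 starters (6%, 11% and 22% of the sample) average about 6, 12 and 23 months, but lost late switchers offset them.

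**2. Changing starts.** If starts change as exp(g·t), the pooled density becomes f(d)·exp(−g·d). For exponential f with rate k, the mean is 1/(k + g). With k = 1/6:
- starts rising 20% a year: g = ln(1.2)/12 = 0.0152, mean 1/(0.1667 + 0.0152) = 5.50 against 6;
- starts falling 20% a year: g = ln(0.8)/12 = −0.0186, mean 1/(0.1667 − 0.0186) = 6.75.

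**3. Recent uptake.** The leaving rate is λ = ln 2/11 = 0.0630 per month. The steady-state mean for switchers is 1/(λ + h): 1/0.0930 = 10.75, 1/0.1130 = 8.85, 1/0.1630 = 6.13. For a start at s and a switch at e within the window, the weight is starts(s) × h(e) × exp(−∫h from s to e) × exp(−λ(e − s)). Pooled mean of e − s in months, with percentage difference from steady state taken before rounding:

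| Switching begins; starts | h = 0.03 | h = 0.05 | h = 0.10 |
|---|---|---|---|
| Always practised; flat | 10.75 (0%) | 8.85 (0%) | 6.13 (0%) |
| 24 months before 2014; flat | 11.22 (+4%) | 9.24 (+4%) | 6.29 (+3%) |
| 12 months before; flat | 11.84 (+10%) | 9.99 (+13%) | 6.96 (+13%) |
| 12 months before; +10% a year | 10.60 (−1%) | 8.99 (+2%) | 6.36 (+4%) |
| 12 months before; +20% a year | 9.70 (−10%) | 8.27 (−7%) | 5.95 (−3%) |
| Jan 2014, at once; flat | 12.94 (+20%) | 11.61 (+31%) | 9.43 (+54%) |
| Linear rise over 2014–2015; flat | 13.45 (+25%) | 12.26 (+39%) | 10.19 (+66%) |

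In the January 2014 row, 25–27% of switchers started before 2014, with mean 4/2 durations of 22–26 months.

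**4. Medians.** Steady-state medians are 7.5, 6.1 and 4.3 months. The January 2014 row gives 8.5, 7.3 and 5.4; uptake 12 months earlier with flat starts gives 7.8, 6.4 and 4.4. Medians move less than means.

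**5. Tempting remedies.** Bounding the 4/2 start at 1 January 2014 leaves only the right-hand truncation: true means of 3, 6 and 12 become 2.82, 5.25 and 8.79 (6%, 12% and 27% short). Taking the headline from starters between January 2014 and June 2016 gives medians of 7.1, 6.0 and 4.2 if switching began at its full rate in January 2014. At h = 0.03, however, that group's mean is 9.5 against 10.75, about 11% short. With a linear rise over 2014–2015 its medians are 8.9, 7.7 and 5.8, against pooled 8.7, 7.7 and 5.8, so nothing is gained.

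**The case against.** The strongest reply is that sampling on the switch date is unbiased for switchers' 4/2 duration when practice is stable, and that the sign depends on facts the documents omit. That stands: uptake 24 months before the window leaves an excess of only 3–4% with flat starts, and uptake 12 months before with starts rising 20% a year makes the pooled mean too short. It is also fair that the large percentages concern means of skewed data, that section 8.7 plans medians too, and that in the January 2014 scenario medians differ by only 1.0 to 1.2 months, less than one six-week 4/2 cycle.

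The study is also descriptive, uses a convenience sample, and leaves detail to a statistical analysis plan. That lowers the stakes but does not close the gap: the subgroup provision does not commit to a split by 4/2 start date, and the stated limitations stop at post-switch outcomes. Stability cannot simply be assumed either, since section 7 itself describes switching as recent.

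**Conclusion.** The point holds as a conditional one. The pooled 4/2 duration and time to switch depend on the calendar window, and the plan neither shows nor discloses this. In the recent-uptake rows above, the pooled mean lies between about 10% too short and about 65% too long. That range belongs to those assumptions. Faster switching widens it: at 1/6 per month from January 2014 with flat starts, the pooled mean is 7.89 against 4.35, or 81% too long. Falling starts push the pooled mean further upward.

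A reader might infer more, in three ways that the documents do not support:
- That 4/2 duration will certainly be overstated. Without an adoption date, switch rate or trend in starts, neither size nor net direction can be fixed.
- That pre-2014 starters must still have been taking 4/2 in 2014. Because gaps are allowed, the condition is only that the switch came in 2014 or later.
- That post-switch outcomes are enriched for long-term responders. The calculation uses identical patients with constant rates and cannot show this, and the documents offer no evidence for it.

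This is a cheap improvement to reporting, not a defect in eligibility.

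**What to change.** Keep the eligibility window, all patients and the pooled summary. Add to section 8.7:

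- Time to switch, duration on 4/2 and baseline characteristics of switchers will also be tabulated by period of 4/2 start: before 1 January 2014; 1 January 2014 to 30 June 2016; 1 July 2016 to 30 June 2018. Medians lead, and the share starting before 2014 is shown.
- The pooled figure is labelled as conditional on switching within the window.
- If a country's window changes under criterion 3a, the period boundaries move with it. State whether this split counts toward the two-subgroup limit.

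Add the selection to the limitations in section 8.9. Do not bound the 4/2 start alone, and do not replace the pooled headline with the middle group, which is distorted if uptake was gradual after 2014 and is still right-truncated.

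The cost is wording and one extra table split; the dates are already to be collected. The downside is small groups: in the January 2014 scenario, if all 150 records were switchers, the earliest group would hold about 38 to 41 (0.25 × 150 to 0.27 × 150), and fewer under the other scenarios tabulated.
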